TITLE

Operator Radiation Exposure for Right vs Left trans-radial catheterization. **Hyper Adduction of Right Radial Artery/Arm vs left arm drag over technique, HARRA study.**

Unique Protocol ID: 2022-05-19

Document Date: October 14, 2022

INTRODUCTION, BACKGROUND AND SIGNIFICANCE:

Several studies have evaluated operator and (patient) exposure comparing left and right transradial approaches. The TALENT study by Schiabasi et al concludes left radial approach for coronary diagnostic procedures is associated with lower fluoroscopy time and radiation dose adsorbed by patients compared with the RRA, particularly in older patients and for operators in training. This study laid the foundation examining different radiation doses comparing left and right transradial approaches. Subsequent studies (OPERA, RAD-MATRIX) examined operator dose favoring LRA procedures. However the primary access point for interventional cardiologist is the RRA due to catheterizations laboratories historically set up for the operator to work from the right side of the fluoroscopic table which makes it a more ergonomic procedure. In light of new data elucidating that an adducted right arm yields lower amounts of operator exposure compared with an abducted arm we seek to determine if this technique will yield similar operator radiation exposure comparing an adducted right radial artery approach to a left radial artery approach.

STUDY OBJECTIVES

- Studying the difference between radiation exposure to primary operator for diagnostic coronary angiography procedure with right transradial access in HARRA position versus standard left transradial access.
- Evaluating the radiation exposure difference between right and left eye of the primary operator
- Studying the total fluoroscopic time and patient's radiation exposure during the diagnostic coronary angiogram and its relationship to presence of subclavian artery tortuosity

HYPOTHESIS

Several studies have shown that operator exposure via left transradial catheterization has yielded less operator exposure compared to standard right transradial procedure. However, in light of new data, we hypothesize a hyperadducted right arm during right transradial cardiac catheterization will yield comparable, or the same operator radiation exposure.

STUDY DESIGN

Randomized, non-blinded prospective study

Subjects: Explain who potential subjects are, where they will be recruited, etc.:

- **All the Cardiac Catheterization Laboratory (CCL) physician operators who consent to participate in the study are the primary study subjects**
- **7-10 CCL physician operators will participate in the study as the primary study subjects**
- **Patients undergoing the procedure will be secondary study subjects only**
- **Sample size for secondary study subjects: 534 patients of any sex and gender and Age > 18 years old**

- **Patients seen at Maimonides Medical Center, who meet the inclusion criteria**

Eligibility Criteria: Include inclusion and exclusion criteria.

Inclusion Criteria:

- All the Cardiac catheterization laboratory physician operators who consent to participate in the study
- Patients of any sex and gender.
- Age > 18 years old.
- Patients undergoing diagnostic coronary angiogram from in-patient and out-patient settings

Exclusion Criteria:

- History of prior CABG (Coronary Artery Bypass Surgery). CABG patients will be excluded due to inherent increased fluoroscopic time (finding grafts).
- Patients undergoing elective PCI (Percutaneous Coronary Intervention)
- Patients that have cognitive dysfunction

Data Collection Procedures:

Variables to be collected include:

Operator variables

- Primary operator's radiation exposure at the end of a case at four sites: right and left eye, thorax and abdomen
- Primary operator's normalized radiation dose exposure, measured by dividing cumulative dose by dose area product (CD/DAP)
- Primary operator's height, weight and body surface area

Patient variables

- medical record number
- dose area product (cGy.cm²) [radiation to patient]
- fluoroscopy time (minutes)
- amount of contrast delivered in cc's
- Milligray [radiation to patient]
- number of cineangiograms taken
- number of diagnostic catheters used for the exam
- age
- sex (female, male)
- race/ethnicity (white, black, Hispanic, East Asian (Chinese etc.), South Asian (India, Pakistan & surrounding areas), other
- height measured in centimeters
- weight measured in kilograms
- body mass index

- body surface area
- hypertension
- diabetes
- smoker
- previous coronary angiography
- chronic kidney disease
- distal radial approach used
- Presence of subclavian artery tortuosity

Statistical analysis:

Sample size:

- **Number of CCL physician operators as the primary study subjects: 10**
- Estimated number of participants to be screened as secondary study subjects: 1500
- Eligible participants to be included as the secondary study subjects in the study: 534
- Calculation for power analysis: Sample size was calculated using data from a previous study (Dominici et al., 2013). Left radial artery values were M=33, SD=37 μ Sv and right radial artery values were M=44, SD=32 uSV. Calculations were performed for a Mann Whitney test due to skewed data with alpha=0.05, power=0.90, a balanced study design, with a two tailed test, and adding 10% to each group for sample size for people who start the procedure but due to difficulty in catheter placement then cannot continue the procedure and need to use a different access site. This results in 267 participants for each of the left radial artery and right radial artery groups for a total of 534 participants.

Data Analysis:

- Biostatistician will be analyzing de-identified data and will guide statistical interpretation
- Descriptive statistics of mean and standard deviation will be used for the continuous variables. Frequency and percentage will be used for the categorical variables. Inferential statistics of the Mann Whitney test will be used to compare μ Sv values in operators between the left radial artery and right radial artery groups.

Expected Outcomes: Explain what you hope the study will determine.

We expect to find that using hyperadduction technique of the right arm can make operators radiation exposure from the hyperadducted right radial approach is less. The objective of this study is superiority with a power value of 80%.

References:

1.

Am Heart J. 2011 Jan; 161(1):172-9. doi: 10.1016/j.ahj.2010.10.003.
Transradial approach (left vs right) and procedural times during percutaneous coronary procedures: TALENT study.
Sciahbasi A¹, Romagnoli E, Burzotta F, Trani C, Sarandrea A, Summaria F, Pendenza G, Tommasino A, Patrizi R, Mazzari M, Mongiardo R, Lioy E.

2.

Operator exposure to x-ray in left and right radial access during percutaneous coronary procedures: OPERA randomised study.
Randomized controlled trial
Dominici M, et al. Heart. 2013.
Dominici M¹, Diletti R, Milici C, Bock C, Placanica A, D'Alessandro G, Arrivi A, Italiani M, Buono E, Boschetti E.

3.

JACC Cardiovasc Interv. 2014 Jul;7(7):810-6. doi: 10.1016/j.jcin.2013.11.026. Epub 2014 Jun 18.
Operator radiation exposure and physical discomfort during a right versus left radial approach for coronary interventions: a randomized evaluation.

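### The SAP hypothesises similar operator exposure but declares superiority and plans only a test of difference, so it cannot show what it hypothesises

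*SAP*

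**What the plan says.** Two places in the SAP state an aim of similarity. The Introduction seeks "similar operator radiation exposure comparing an adducted right radial artery approach to a left radial artery approach", and the Hypothesis reads "we hypothesize a hyperadducted right arm during right transradial cardiac catheterization will yield comparable, or the same operator radiation exposure".

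The Expected Outcomes section states a different aim. It expects that "operators radiation exposure from the hyperadducted right radial approach is less" and adds: "The objective of this study is superiority with a power value of 80" per cent. The first item under Study Objectives is neutral and speaks only of studying a difference.

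The statistical sections contain one inferential method: "Inferential statistics of the Mann Whitney test will be used to compare" operator μSv values between the left and right radial groups. The Sample size section specifies "alpha=0.05, power=0.90, a balanced study design, with a two tailed test". Its planning inputs come from an earlier left-versus-right radial study: "Left radial artery values were M=33, SD=37" μSv, against a right radial mean of 44 and SD of 32. After a 10% addition this gives 267 per group, 534 in total. The document states no equivalence or non-inferiority margin, confidence interval or rule for concluding comparability.

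**The concern.** Similar, the same and less are different claims. Superiority is supported by rejecting the null hypothesis of no difference. Similarity is supported by a confidence interval that excludes a difference large enough to matter. A test of no difference cannot do the second job, because failing to reject may reflect imprecision as easily as equality.

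As written, the result that the Hypothesis predicts is the one from which the planned analysis can conclude least. The planning effect does not help either aim. It has right radial exposure higher than left, which is neither equality nor lower exposure with HARRA. At stake is what the trial may claim from its primary comparison.

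**Working it through.** **Inputs, all from the SAP's Sample size section.** Left mean 33, SD 37; right mean 44, SD 32 (μSv); two-tailed alpha 0.05; power 0.90; 1:1 allocation; 10% added per group.

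**1. Reproduce the plan's figure.**
- Difference = 44 − 33 = 11.
- Pooled SD = √((37² + 32²)/2) = √1196.5 = 34.59.
- Standardised difference = 11/34.59 = 0.318.
- A two-sided t-test power calculation, with the Mann-Whitney minimum asymptotic relative efficiency of 0.864, gives 242 per group.
- 242 × 1.10 = 266.2, rounded up to 267. This matches.
- The same calculation at 80% power gives 181 per group, and at most 202 after inflation. So 267 belongs to the stated 0.90, not to the 80% in Expected Outcomes.

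The arithmetic is sound. The trial is sized to detect a difference.

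**2. What the test does if the hypothesis is true.** If the two exposure distributions are the same, a two-sided 0.05 test rejects about 5% of the time and is non-significant about 95% of the time, whatever the sample size.

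**3. What a non-significant result leaves open.** This uses 242 evaluable per arm, a normal approximation on means and independent cases.
- SE = 34.59 × √(2/242) = 3.145 μSv.
- 95% CI half-width = 1.96 × 3.145 = 6.2 μSv, or 6.2/33 = 19% of the left radial planning mean.
- A result just short of significance, with HARRA worse, has an interval from about 0 to 2 × 6.16 = 12.3 μSv. That exceeds the 11 μSv planning gap.

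**4. What the existing size could support if comparability were the aim.** The SAP gives no margin, so the margins here are illustrative. True difference 0, raw scale, one-sided 0.025.
- Smallest non-inferiority margin with 90% power = (1.960 + 1.282) × 3.145 = 10.2 μSv. Allowing for the 0.864 efficiency: 10.2/√0.864 = 11.0 μSv.
- Power for a margin M = Φ(M/SE − 1.96). For M = 5.5 (half the planning gap): Φ(5.5/3.145 − 1.96) = Φ(−0.21) = 0.42. With SE = 3.145/√0.864 = 3.383: Φ(−0.33) = 0.37. So roughly 40%.
- Evaluable n per group for 90% power at M = 5.5, without efficiency loss or inflation: 2 × (34.59 × 3.242/5.5)² ≈ 832.
- For two-sided equivalence with two one-sided tests at 0.025, the smallest margin with 90% power = (1.960 + 1.645) × 3.145 = 11.3 μSv.

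**The case against.** The strongest reply is that the operative text is consistent. The sizing, the single test and the declared objective all concern a difference, and superiority is the only objective type that the SAP names. On that view the Introduction and Hypothesis are loose narrative, a superiority trial needs no margin, and a null result has a valid conclusion: superiority was not shown. Much of this stands. It means that the absent margin is a defect only if comparability is the aim, and that the choice belongs to the sponsor. It does not remove the conflict, because the Hypothesis is the SAP's formal statement of what is expected and it still predicts equality.

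Three stronger readings are tempting, but the document does not support them.

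- *A non-significant p-value will be reported as comparable.* The SAP does not say so. Its Hypothesis invites that reading and nothing in the text rules it out.
- *The existing sample size suffices for non-inferiority, so the change needs no extra patients.* This depends on the margin. For example, a ratio margin of 1.25 can be made to look as if it keeps about half of the left arm's advantage, but only by fitting log-normal distributions with unequal log SDs (0.90 and 0.65), which gives a geometric mean ratio of 1.62. The planning means give 44/33 = 1.33, and ln 1.25/ln 1.33 = 0.78, so the margin would give away about 78% of that advantage. Keeping half of it needs a margin of √1.33 ≈ 1.155, for which power at 240 per arm is about 42% to 52% under the same log-normal approach.
- *The Hypothesis means non-inferiority.* Its wording is closer to two-sided equivalence. Non-inferiority is a reasonable choice because lower exposure is better, but it has to be stated.

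It is also fair to object that step 3 uses normal theory on means, whereas the SAP chose Mann-Whitney because the data are skewed. The boundary of significance may differ somewhat, so the interval widths indicate scale only.

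**Conclusion.** The point holds: followed as written, the plan cannot support its own hypothesis. The Introduction and Hypothesis state similarity, Expected Outcomes states superiority, and the one planned test addresses only a difference. The sample size calculation is internally correct at 90% power. The fault is the mismatch of aim and analysis, together with a planning effect that runs opposite to the expected superiority and a power figure stated as both 0.90 and 80%.

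The figures assume the planning SDs, about 242 evaluable cases per arm, normal theory on the raw scale and independent cases. Exposures come from only 7 to 10 operators, and the document gives no within-operator correlation, so true precision may differ. No conclusion is drawn about whether 534 patients are enough for a comparability aim. That cannot be settled without a margin.

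**What to change.** Choose one primary objective and make the Hypothesis, Expected Outcomes and power statements agree with it, with a single power figure.

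**Under either objective:** report the HARRA-minus-left difference, or the HARRA/left ratio, on a named scale with a two-sided 95% confidence interval. State that a non-significant Mann-Whitney result will not be described as comparable.

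**If superiority is kept:** remove the comparability wording from the Introduction and Hypothesis. State that the planning effect (right higher than left) runs opposite to the expected direction and comes from values labelled simply as right radial, not hyperadducted.

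**If comparability is the aim:** before outcome data are seen, fix a margin that the sponsor justifies, on a stated scale. Declare non-inferiority only if the upper limit of the two-sided 95% confidence interval lies below it. Then test superiority at two-sided 0.05 in fixed sequence, which needs no alpha adjustment. Restate the power that 267 per group gives for that margin.

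**Cost:** alignment and the interval need only SAP text and one added estimate from data already collected. A comparability objective also needs a justified margin and a revised power statement. Whether it needs more patients depends on that margin.

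### The 11 µSv planning difference comes from an earlier left-versus-right study, so the stated 90% or 80% is not the power for HARRA versus left

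*SAP*

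**What the plan says.** Under Statistical analysis, Sample size, the SAP takes its inputs from an earlier left-versus-right radial trial: "Left radial artery values were M=33, SD=37" µSv, and "right radial artery values were M=44, SD=32 uSV". The calculation is for a Mann-Whitney test with "alpha=0.05, power=0.90, a balanced study design, with a two tailed test". Ten per cent is added to each group for procedures that must change access site, giving 267 per group and 534 in total.

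The Study Objectives section sets right access in the HARRA position against standard left access. The Hypothesis section recalls that "operator exposure via left transradial catheterization has yielded less operator exposure compared to standard right transradial procedure", and then predicts that hyperadduction will bring right-sided exposure level with left.

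Expected Outcomes goes further. It anticipates that hyperadduction "can make operators radiation exposure from the hyperadducted right radial approach is less", without saying less than what, and adds: "The objective of this study is superiority with a power value of 80" per cent. The SAP gives no exposure value for HARRA, no HARRA-versus-left difference and no margin.

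**The concern.** A power statement holds for a particular true difference. The only difference used here is left lower than right by 11 µSv, from a study that the Introduction counts among those favouring left. HARRA is being tested because adduction is expected to lower right-sided exposure, so the intervention is meant to shrink the very gap used for sizing. The hypothesis puts the difference at about zero. The expected outcome, if it means less than left, gives it the opposite sign.

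The practical risk lies in how the result is read. If HARRA and left are truly alike, the likely result is a non-significant Mann-Whitney test. With 90% power printed in the plan, that result could be taken as proof of comparability. A superiority test with no margin cannot supply such proof.

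**Working it through.** **Inputs** (Statistical analysis, Sample size): means 33 and 44 µSv; SDs 37 and 32; two-sided alpha 0.05; power 0.90; 1:1 allocation; 10% added.

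**1. Reproducing 534**
- Difference: 44 − 33 = 11 µSv.
- Pooled SD: √((37² + 32²)/2) = √1196.5 = 34.59.
- Standardised difference: 11/34.59 = 0.318.
- Two-sample t-test at 90% power: 208.8 per group. The normal approximation, 2(1.960 + 1.282)²/0.318², gives 208.
- Divided by 0.864, the minimum asymptotic efficiency of Mann-Whitney relative to the t-test: 241.6, rounded up to 242.
- Adding 10%: 242 × 1.10 = 266.2, rounded up to 267 per group, 534 in total. This matches exactly.
- With 80% power, the same route gives 199 to 201 per group, depending on how the 10% is applied. Of the two stated powers, only 0.90 yields 534.

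**2. What 534 delivers**

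Take about 240 evaluable per arm (267 × 0.9 = 240.3) and SD 34.59 in both arms. The standard error is 34.59 × √(2/(240 × e)), where e is the efficiency: 3.16 for e = 1 and 3.40 for e = 0.864. Power is Φ(difference/SE − 1.96), plus a negligible opposite tail except near zero.

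| True difference, either direction | Chance of a significant result |
|---|---|
| 0 (the hypothesis) | 5%, of which 2.5% favours HARRA |
| 5.5 µSv (assumed, not in the SAP) | Φ(5.5/3.40 − 1.96) to Φ(5.5/3.16 − 1.96) = 37% to 41% |
| 11 µSv (the planning gap) | Φ(11/3.40 − 1.96) to Φ(11/3.16 − 1.96) = 90% to 94% |

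If left really is lower by 11 µSv, the chance of a significant result favouring HARRA is about zero. For about 90% power to show HARRA lower than left, with left at 33, HARRA would have to average about 33 − 11 = 22 µSv, half of the right-sided 44 in the SAP.

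**3. If the aim is comparability**

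With true equality and a one-sided 2.5% non-inferiority test, power is Φ(margin/SE − 1.96). At e = 0.864 an 11 µSv margin gives about 90%. Over the same efficiency range a 5.5 µSv margin gives about 37–41%. Both margins are illustrations, as the SAP states none.

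**The case against.** A reader might infer that 534 is powered only to show left lower than HARRA, so that the stated power is simply the chance of finding HARRA worse. The SAP does not support that. It specifies the calculation "with a two tailed test", so with similar SDs an 11 µSv difference in HARRA's favour has the same power of about 90%. The sign of the planning gap does not by itself void the calculation.

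A reader might also infer that the SAP assumes HARRA brings no benefit. It says only that earlier data were used, and never predicts 44 µSv for HARRA. Borrowing a published gap and SDs is common when a new technique has no data, and it has a sensible reading here: if the old gap persisted, the trial would detect it. The Study Objectives wording, a difference between the two approaches, has no direction and suits a two-tailed test.

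Two further points are fair. The expected outcome names no comparator, so less could mean less than a conventional right approach; but the SAP describes no such arm, so this reading would not tie the calculation to the trial's comparison. And a 5% rejection rate at equality is true of every two-sided 5% superiority test at any size. It reflects the choice of objective and is not an error in 534.

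What remains is that the SAP does not justify 11 µSv as a HARRA-versus-left difference, and that hypothesis, objective and sample size answer different questions.

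**Conclusion.** The point holds in this limited form. The figure 534 is correctly calculated and gives about 90% power for 11 µSv in either direction. The SAP offers no reason to expect a difference of that size between HARRA and left, and its own hypothesis expects none. Neither "alpha=0.05, power=0.90" in the calculation nor the 80% under Expected Outcomes is therefore the power for the trial's question. At the hypothesised equality the chance of a significant result is 5%, and only 2.5% in HARRA's favour.

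The figures assume about 240 evaluable per arm, the earlier study's SDs in both arms whatever the HARRA mean, a Mann-Whitney efficiency between 0.864 and 1, and independent procedures with no clustering by operator. The 5.5 µSv scenario is an illustration. The statement that the planning gap runs against the expected outcome depends on reading less as less than left, which the superiority sentence suggests but does not say.

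**What to change.** Keep 534 and rewrite the power paragraph together with the Expected Outcomes sentence:

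- Label 33 and 44 µSv as values from an earlier left-versus-right comparison, not HARRA values.
- Replace the conflicting 0.90 and 80% with one statement: with about 240 evaluable per arm, SD 34.6 and efficiency 0.864, power is about 90% for 11 µSv in either direction and about 37% for an assumed 5.5 µSv (41% at efficiency 1); at equality the chance of significance is 5%, 2.5% favouring HARRA.
- State one objective, and name the comparator for less exposure.
- If the objective is comparability, as hypothesised, prespecify and justify a non-inferiority margin, report a confidence interval for HARRA minus left, and give power at true equality for that margin.
- State that a non-significant superiority test will not be read as comparability.

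The cost is a short rewrite and a less favourable power figure for superiority. It cannot be promised that no more patients would be needed for comparability: at an 11 µSv margin 534 would serve, at 5.5 µSv it would not.

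### The 10% sample-size allowance implies that patients who switch access site leave the primary comparison, although their operator dose is recorded and the SAP sets no rule for them

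*SAP*

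**What the plan says.** The power calculation under Sample size uses "alpha=0.05, power=0.90, a balanced study design, with a two tailed test" for a Mann-Whitney test. It then enlarges both groups by 10% to allow for "people who start the procedure but due to difficulty in catheter placement then cannot continue the procedure". These are the patients who, in the SAP's words, "need to use a different access site". The result is 267 per group, 534 in all.

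Data Analysis says only that a Mann-Whitney test compares operator µSv values between the left and right radial groups. It does not say whether a patient belongs to the randomised group, to the access finally used, or to neither after a switch.

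Data Collection Procedures has the primary operator's exposure read at the end of each case. Study Design describes the trial as randomised and not blinded.

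**The concern.** The only statement the SAP makes about switched patients is in the sample size, and there they are treated as losses to be replaced. They are not losses in the usual sense. The case goes on through another site, and the operator's dose is still read at its end. The switch happens after randomisation and because the assigned access could not be used, so it is part of what that access strategy costs the operator.

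If such cases are left out, the arms are no longer compared as randomised. If one access fails more often, or its failures carry more dose, leaving them out makes that arm look better than it is. The Hypothesis section expects exposure in the hyperadducted right arm to be about equal to the left, so a hidden excess on either side bears on the conclusion. Operators know the allocation, decide when to abandon an access, and are the people whose dose is measured. The rule should therefore be fixed in advance.

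**Working it through.** **Inputs from the SAP, Sample size.** "Left radial artery values were M=33, SD=37" µSv; "right radial artery values were M=44, SD=32 uSV"; two-sided alpha 0.05; power 0.90; 1:1 allocation; 10% added per group.

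**Assumed, because the SAP gives no figure.** Switch rates by arm, the dose multiplier m in a switched case, and a lognormal shape for dose. The Mann-Whitney efficiency is not stated either; 0.864 (the minimum asymptotic relative efficiency) is the value that returns the SAP's figure.

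**1. Reproducing 267.**
- Pooled SD = √[(37² + 32²)/2] = √1196.5 = 34.59; difference = 44 − 33 = 11; standardised difference = 11/34.59 = 0.318.
- Two-sample t-test: 209 per arm. Mann-Whitney: 209/0.864 = 241.9, so 242.
- 242 x 1.10 = 266.2, so 267, an exact match.
- At 80% power, the figure under Expected Outcomes, the same route gives 181 x 1.10 = 199.1, so 200. Only 0.90 fits.

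The calculation therefore needs 242 evaluable cases per arm and adds 25 to stand in for switched ones.

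**2. Hidden excess on the mean scale.** Let completed cases average 33 µSv in both arms. Then the arm mean = 33 x [(1 − p) + p x m], and the true excess = 33 x (p1 − p2) x (m − 1). Dropping switchers reports about 0 in every row.

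| Switching, arm 1 vs arm 2 | m = 2 | m = 3 |
|---|---|---|
| 10% vs 10% | 0 | 0 |
| 5% vs 3% | 0.66 µSv | 1.32 µSv |
| 10% vs 3% | 36.30 − 33.99 = 2.31 µSv | 39.60 − 34.98 = 4.62 µSv |
| 15% vs 5% | 3.30 µSv | 6.60 µSv |

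For 10% vs 3%, this is 21% to 42% of the 11 µSv planning difference.

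**3. The same scenario on the planned test.** Simulation used lognormal dose, mean 33, SD about 35, 267 per arm, and 10% vs 3% switching.
- All cases kept: Mann-Whitney rejects about 9% to 10% of the time at m = 2 and about 14% to 16% at m = 3. The median difference is about 1.1 to 1.6 µSv, and the chance that a case in the arm with more switching exceeds one in the other arm is 0.515 to 0.522.
- Switchers dropped: it rejects about 5% of the time.
- At 5% vs 3% switching: about 5% to 6% either way.

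**4. Power.** On the basis of step 1, 267 per arm gives about 92.6% if all cases are analysed. After a 10% loss, 267 x 0.9 is about 240 per arm, which gives 89.8%. If all are kept and switching dilutes the difference by an assumed 10% to 9.9 µSv, 267 gives about 87%, and 90% would need about 242/0.9² = 299 per arm.

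**The case against.** **Exclusion is inferred.** A reader might infer that the SAP excludes switched cases. It does not say so. The allowance points that way and no analysis set contradicts it, but a planner could also add a margin against dilution while keeping every case. The protocol is not at hand and may settle the matter. This stands, and limits the point to an implied exclusion that the SAP leaves open.

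**Nothing shows that failed cases carry high exposure.** A reader might take this as given. The SAP has no dose, fluoroscopy time or switch rate for them, and an attempt abandoned before much imaging could add little. The objective on fluoroscopic time and patient dose and their "relationship to presence of subclavian artery tortuosity" does not concern switching and is no support. The exclusion of prior bypass patients for longer fluoroscopy makes higher dose in difficult cases plausible, no more. This stands.

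**The mean scale overstates the effect on the primary result.** The only inferential test is Mann-Whitney, which reacts weakly to a few inflated values. This stands: 21% to 42% of the planning difference describes means and does not say how often the trial's conclusion would change.

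**The power loss is no defect.** Falling from 92.6% to 89.8% is the allowance doing what it was meant to do. This stands.

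None of this answers the core point. Leaving out observed outcomes because the assigned access failed departs from the randomised comparison, and the SAP's only guidance leans that way.

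**Conclusion.** The point holds in limited form. The 267 is internally sound as 242 plus 10%, but the reason given for the 10% implies that switched cases do not count, and the analysis text does not correct this.

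The direction of any bias favours the arm with more, or more exposed, failures. Its size rests wholly on assumed switch rates and dose multipliers: zero with equal rates and equal failed-case doses, and 2.3 to 4.6 µSv in means for 10% vs 3% switching at 2 to 3 times the dose. On the Mann-Whitney test the same excess would usually go undetected even with all cases kept, so the likely effect is more on the reported estimates than on the significance result. That makes it a change that should be made, short of one that must be made before the trial can be interpreted.

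**What to change.** In Data Analysis, state that:
- the primary Mann-Whitney comparison includes every randomised patient in the assigned arm;
- the outcome is the operator's total end-of-case dose, covering the failed attempt and the second access;
- the number and proportion of switches are reported by arm;
- a completed-as-assigned analysis is given as a sensitivity analysis.

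In Sample size, state that the 10% is no longer a loss allowance for switchers, and that 267 per arm gives about 92.6% power with all cases analysed, before any dilution from switching.

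The cost is wording. Dose is already read when the case ends, and the planned number can stay. The downside is small: switched cases add variability and may dilute the contrast between access routes, to about 87% power if the difference fell to 9.9 µSv.
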